# CHAPTER 1. INTRODUCTION

[figure not shown]
Older adults spend the majority of their day engaging in sedentary behavior, which increases risk of mortality by 22%. Despite the well-established health benefits of physical activity, a large portion of older adults remain sedentary. Recent evidence suggests that inflammation contributes to lack of motivation, which is a critical barrier to overcoming sedentary behavior in older adults. Given that inflammation is highly modifiable by diet, an anti-inflammatory dietary strategy may be a viable way to improve inflammation-driven lack of motivation and ultimately increase physical activity in sedentary older adults. However, interventions targeting such a pathway are scarce. This proposal's objective is to determine the feasibility and preliminary efficacy of daily supplementation of freeze-dried blueberry which provides 2 anti-inflammatory nutrients (fiber and anthocyanins) to modulate inflammation-driven lack of motivation. We propose a single-site, randomized, double-blind, parallel pilot study in 40 sedentary, older adults with depressive symptoms. Individuals with depressive symptoms often have lack of motivation and increased levels of inflammatory cytokines, representing an ideal population for an anti-inflammatory intervention targeting to improve motivation. Participants will be randomized to consume either 48 g of freeze-dried blueberry powder (~600 mg of anthocyanins and ~8 g of fiber) or a nutritionally matched placebo powder (devoid of anthocyanins and fiber) each day for a total of 12 weeks. Identification of a dietary intervention to target the inflammatory pathways may offer a novel and feasible approach to increase motivation and increase the engagement of physical activity in older adults. If feasible and effective, such a strategy would help avoid the plethora of health consequences associated with sedentary behavior and physical inactivity.

# CHAPTER 2. BACKGROUND

Sedentary behavior and physical inactivity are associated with serious health consequences. A meta-analysis of 13 studies report that higher sedentary time is associated with a 22% higher risk of all-cause mortality. Thus, sedentary behavior is a pressing public health concern that has direct impact on the well-being of the aging population. Although there are several determinants of sedentary behavior in older adults, lack of motivation is a significant contributor. Thus, in order to increase physical activity in sedentary older adults, one must first modulate the motivation to engage in goal-directed behavior, such as physical activity; doing so may help **ameliorate the higher risk of mortality associated with sedentary behavior** in older adults.

Markers of inflammation have been linked with behavioral features of sedentary behavior, such as physical fatigue and lack of motivation (**Figure 1**). Inflammation has been shown to modulate dopamine activity, which results in lack of motivation. Targeting inflammation holds great promise to ameliorate the lack of motivation in sedentary older adults and improve the downstream effects on engagement in physical activity. Since inflammation is a key contributor to most age-related diseases, the results from this proposal could identify **new therapeutic strategies for other age-related diseases that feature inflammation as a central aspect of pathogenesis**.

Figure 1. Conceptual Model

Brain-derived neurotrophic factor, BDNF; C-reactive protein, CRP, Interleukin-6, IL-6;

It is well-known that inflammation is highly modifiable by diet. Anthocyanins are pigments found in fruits and vegetables that are responsible for the blue/purple colors. Both anthocyanins and dietary fiber have anti-inflammatory properties. However, older adults typically consume low quantities of both anthocyanins and fiber. Thus, such quantities may not be sufficient to harness the anti-inflammatory benefits. A plethora of

interventions supplementing berries/berry products (a concentrated source of fiber and/or anthocyanins) reduced markers of inflammation in various populations (age range: 20-70 y, including healthy individuals and those with diabetes, obesity, osteoarthritis etc.). Older adults with depressive symptoms, who typically have high levels of inflammatory cytokines, may be particularly responsive to an anti-inflammatory dietary intervention. Since fruits and vegetables are a rich source, fiber and anthocyanins can be easily obtained at grocery stores and are widely accessible to a large portion of older adults.

Despite consistent evidence that diet modulates inflammation and inflammation is linked to lack of motivation, to our knowledge no dietary interventions have supplemented anti-inflammatory nutrients to target motivation and physical activity. Fiber and anthocyanins are known for their anti-inflammatory capacity, and may be a viable supplemental strategy to reduce inflammation and improve motivation. The findings from this proposal will yield preliminary data on variation of change in motivation and aspects of physical activity needed to design a larger, more robust subsequent trials designed to establish definitive efficacy of a fiber and anthocyanin intervention to increase physical activity in sedentary older adults.

## CHAPTER 3: RESEARCH DESIGN

### 3.1 Study Objectives and Aims

The overall objective of this study is to gather preliminary evidence on the feasibility and effectiveness of an intervention supplementing fiber and anthocyanins to usual diet compared to control (placebo). We will conduct a 3-month, double-blind randomized, parallel-arm, pilot study in 40 sedentary, older adults with depressive symptoms that is designed to improve inflammation, motivation, and consequent engagement in physical activity. Our specific aims are:

**Aim 1:** Determine the feasibility of an intervention supplementing usual diet with fiber (8 g/day) and anthocyanins (600 mg/day). We hypothesize at least 80% of the participants enrolled will complete the 3-month intervention.

[figure not shown]
**Aim 2:** Gather preliminary evidence on the impact of fiber and anthocyanin supplementation on relevant inflammatory markers. We hypothesize markers relevant to inflammation (interleukin-6, C-reactive protein, and brain-derived neurotrophic factor) tend to reduce after 3 months of fiber and anthocyanin supplementation compared to control.

**Aim 3:** Obtain preliminary evidence on the efficacy of fiber and anthocyanin supplementation to improve the engagement in physical activity, and further determine if this effect is mediated by change in motivation (via Motives for Physical Activities Measure-Revised questionnaire). We hypothesize the physical activity (i.e., average daily step count via accelerometer) tends to increase after 3 months of fiber and anthocyanin supplementation compared to control, and that a substantial portion of this effect is mediated via an increase in motivation.

Our overall hypothesis is that a 3-month dietary intervention supplementing fiber and anthocyanins in sedentary, older adults with depressive symptoms will be feasible and demonstrate preliminary efficacy.

### 3.2 Overview

This will be an individual-level, double-blind, randomized, parallel pilot study in 40 sedentary, older adults with depressive symptoms. Screened and eligible participants will perform baseline assessments and provide a blood sample. Next they will be randomized to consume either blueberry powder (which provides ~8 g/day of fiber and ~600 mg/day of anthocyanins) or placebo powder (nutritionally matched powder without anthocyanins or fiber) for 3 months (**Figure 2**).

### 3.3 Inclusion and Exclusion Criteria

Our target population is sedentary older adults, with minor depressive symptoms. Individuals expressing an interest in participating after recruitment out-reach will be screened in-person (e.g., at HRC or at participant's home). Participants will complete several assessments to confirm that they meet the following inclusion criteria.

#### Inclusion Criteria

- Men and women aged  $\geq 65$  years
- Self-reporting  $\geq 8$  hours of sitting per/day (e.g., sedentary behavior)
- Depressive symptoms (defined as  $\geq 4$  and  $< 16$  points on the center for epidemiological studies depression-scale)

Exclusion criteria have been selected to ensure safety and optimize compliance, while minimizing confounds due to overt disease or conditions that may significantly influence study outcomes. Given that this is pilot a study, select criteria will be per discretion of the principal investigator. Exclusions may be during the telephone or in-person screening as described below:

#### Exclusion Criteria

- Unwilling to follow the study protocol
- A median daily step count  $> 7,500$  steps per day (as measured by the ActiGraph), or per discretion of the PI
- Cognitive impairment (defined as Montreal Cognitive Assessment, MoCA  $< 22$  points)
- Self-reporting a history of inflammatory bowel disease/syndrome, major depression, bipolar, schizophrenia, or other psychotic disorders, or per discretion of the PI
- Self-reporting type 1 or type 2 diabetes
- Allergic to intervention or control products
- Recent use (within the last 3 months) of antibiotics or pro-biotics, or per discretion of the PI
- Current substance use disorder (Drug Abuse Screening Test, DAST-10  $> 2$  points)
- Current alcohol use disorder (Alcohol Use Disorders Identification Test - Consumption, AUDIT-C  $\geq 4$  points)
- Unstable anti-depressant use (e.g., change in medication within last 3-6 months), or per discretion of the PI
- Current homicidal or suicidal ideation (assessed via the P4 Suicidality Screener)
- Current psychosis (via the Psychosis and Hallucinations Questionnaire, PHQ  $> 12$  points)
- Manic symptoms (assessed by the Mood Disorder Questionnaire, MDQ  $> 5$  points)

### 3.4 Number of Subjects and Study Duration

We aim to recruit a total of 40 individuals (both men and women), in proportion to the gender and racial distribution of the greater Boston population, through local newspaper and internet advertisements, physician referrals, our registry of research volunteers, Hebrew SeniorLife (HSL) senior housing sites, and patient registries (e.g., HRC or Beth Israel Deaconess Medical Center). Participants will remain in the study for a total of 14 weeks.

### 3.5 Study Endpoints

Primary Outcomes – The primary outcome for this study will be engagement in physical activity.

1. **Engagement in Physical Activity:** Engagement in physical activity will be evaluated by the median # of steps per/day (via ActiGraph) of the previous two weeks before each visit (e.g., 2 weeks before baseline or 2 weeks before follow-up). We will also evaluate median sedentary minutes/day of the previous two weeks before visits.

Secondary Outcomes – We will evaluate several secondary outcomes including:

1. **Feasibility** : Feasibility will be defined as participant retention rate (i.e., number of participants that complete the intervention/total randomized).
2. **Inflammatory Biomarkers:** Serum markers relevant to inflammation, (serum brain-derived neurotrophic factor, BDNF; C-reactive protein, CRP; interleukin-6, IL-6) at baseline and follow-up will be measured by Quest Diagnostics or our collaborators at the University of Connecticut Metabolic Phenotyping Lab.
3. **Motivation:** Motivation to engage in physical activity (our proposed mediator between inflammation and physical inactivity) will be assessed by the self-report questionnaire Motives for Physical Activities Measure-Revised that has been used in middle-aged and older adults.

### 3.6 Study Intervention Products

Given that 100% purified anthocyanins are not commercially available, we will utilize a dietary source of anthocyanins. Blueberries are one of the richest sources of dietary anthocyanins and also conveniently concentrated with fiber. To allow for blinding, we will use freeze-dried powdered blueberries as our intervention product. The powder will be provided by the U.S. Blueberry Council. The placebo powder will also be provided by the U.S. Blueberry Council, which is a nutritionally matched powder except it contains minimal amounts of anthocyanins and fiber. The placebo powder will be labeled with either a letter or number that is different from the intervention powder. This is a double-blind intervention, so neither the participants nor the study staff will know which powder is the placebo and/or which is the blueberry powder. See §5.3 for further information on dietary intervention.

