## **CHAPTER 4 RECRUITMENT AND DATA COLLECTION**

### 4.1 Recruitment Overview

Participants will be recruited from the Boston area community, including senior housing facilities in urban/suburban areas and research recruitment repositories. We will utilize a multi-pronged approach to meet our recruitment goals:

- We will recruit from the research repository that resides at HRC
- We will connect with social workers in and outside the HRC
- We will perform medical record reviews to identify potentially eligible individuals at the Hebrew SeniorLife (HSL) geriatric medicine practices.
- We will advertise through direct mailings to all residents of HRC's seven supportive housing facilities (over 3,000 residents).
- We will give presentations at each Hebrew SeniorLife (HSL) facility.
- We will use the Harvard Catalyst (CTSA) Shared Health Research Information Network (SHRINE) to identify volunteers from Harvard-affiliated hospitals and clinics.
- We will advertise our study within numerous local media outlets, on HRC's Hinda and Arthur Marcus Institute for Aging Research and other websites (e.g., Craig's List), and at [www.clinicaltrials.gov](http://www.clinicaltrials.gov).

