## 4.2 Recruitment Timeline

Our trial proposes to enroll 40 persons over approximately 6-months. We will recruit for two waves of our intervention. For the first wave of the intervention, we aim to recruit 16 individuals over ~3 months. The 16 individuals will then be randomized to the intervention or control group, and participate in the study for 3 months. During the 3 months the first wave of participants are on the study intervention, we will be recruiting for the second wave (n=24) of the intervention. Once the second cohort of 24 individuals is recruited, they will begin the study intervention as soon as possible. To stay on target, we need to recruit ~7 participants/month. Thus, based on our known research participation rates, and the expected prevalence of depressive symptoms in older adults, we will readily be able to meet our recruitment goal of 40 participants.

There will be two waves of the intervention (n=16 for the first wave, and n=24 for the second wave). For each wave, half of the participants will be randomized to the intervention group and the other half will be in the control group. In an attempt to account for the impact of seasonal variation on physical activity levels, we will employ block (blocks of 4) randomization. For every block of 4 participants, 2 will be randomized to consume the placebo powder and the remaining 2 will be randomized to the blueberry powder.

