#### 4.6 Minimization of Bias

This study is designed as a double-blind intervention so neither staff nor participants are aware of their assigned intervention arm. Additionally, to minimize analyst bias, biomarkers will be de-identified and analyzed by technicians unfamiliar with the participants or study phase.

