### 5.3 Dietary Intervention

The duration of this study will be a total of 14 weeks. The first two weeks will require participants to avoid eating certain foods (e.g., fiber- and anthocyanin-rich foods) while also monitoring their usual physical activity with the ActiGraph just prior to the intervention period.

Individuals will then be randomized to either the intervention or the control group. This is a double-blinded study, so the study staff nor the participant will know what powder the participants are assigned to. Those randomized to the intervention group will be asked to consume approximately 48 g of freeze-dried blueberry powder as a source of ~8 g of fiber and 600 mg of anthocyanins. The proposed dose of 48 g of freeze-dried blueberry powder is equivalent to approximately 2 cups of whole blueberries. Individuals randomized to the control group will be asked to consume approximately 48 g of a nutritionally matched placebo powder that is devoid of anthocyanins and fiber.

The powders will be individually packaged in 24 g amounts. Participants will be instructed to consume 2 packets of their respective powder each day for 12 weeks. Participants will be provided with suggestions/recipes on how to consume the powder (for example, mixed in 12 fl oz of water or mixed in 12 fl oz of almond milk). At the beginning of the study the participants will be given a sample of materials (e.g., mixing apparatus) or ingredients (e.g., almond milk) that participants will be able to use to make the suggested recipes they were provided with. It is recommended that participants consume their powder all at once. Given that intervention and control products are regularly consumed, we do not anticipate any toxicities.

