## **6.4 Statistical Power**

The sample size for our pilot study has been chosen to provide a practical basis for developing variance measures of motivation and engagement in physical activity that will be needed to design a subsequent larger randomized controlled trial. The daily step count was the outcome that this study power calculation was based off of. Since studies have not yet evaluated change in step count in response to an anti-inflammatory strategy in our specific population (older, sedentary adults with depressive symptoms), the variations of change that are gathered from this study will be used to estimate power for large scale efficacy trials. Regardless, we have estimated the standard deviation of change in steps utilizing the variation of steps in older, sedentary adults without depressive symptoms previously published. Assuming SD of change=1045, 80% power, and an alpha=0.05, a sample size of 18/group is required to detect a change of 1000 steps/day. An increase in 1000 steps per day was associated with a 16% reduced risk in all-cause mortality. Thus, to account for attrition, we propose a sample size of 20/group. Additionally with a sample size of 20/group, we will also have 73% power (assuming SD of change=41) to detect a change of 30 min/day of sedentary time. Such a change is noteworthy epidemiological evidence suggests that 30 min/day of sedentary time is associated with 17% increased risk of all-cause mortality in sedentary older adults.

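### Section 3.6 appears to give each arm one shared powder code, so decoding a single label could, at worst, unblind all 40 participants

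*Combined protocol and SAP*

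**What the plan says.** Section 3.6 (Study Intervention Products) sets the label: "The placebo powder will be labeled with either a letter or number that is different from the intervention powder". It goes on to say that "neither the participants nor the study staff will know which powder is the placebo". Section 4.6 (Minimization of Bias) relies on this: "This study is designed as a double-blind intervention so neither staff nor participants are aware of their assigned intervention arm". The only further measure there concerns the laboratory: biomarker samples are de-identified, and the technicians do not know the participants. Section 5.3 restates that the study is double-blind and adds no labelling detail.

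Other sections show who comes into contact with the labels and what those people also do:

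- Section 5.2: participants receive their powder at the baseline visit and bring used and unused packets back so that compliance can be estimated. Table 1 places compliance at weeks 4, 6, 8 and 12.
- Section 5.3: powder comes in 24 g packets. "Participants will be instructed to consume 2 packets of their respective powder each day for 12 weeks".
- Section 8.2: gastrointestinal symptoms are recorded at every visit, and the section notes that a sudden rise in fiber, which only the blueberry arm receives, may cause them.
- Section 8.4: severity and relatedness of adverse events are judged by the PI, the study psychiatrist and/or a trained staff member.
- Sections 4.2 and 6.4: two waves of 16 and 24, split equally between arms; "we propose a sample size of 20/group".

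**The concern.** Section 3.6 protects one fact only: which code stands for placebo. It does not hide which participants share a powder. Under two arm-level codes the whole blind hangs on that one fact, and everyone who handles packets can see which of the two groups each participant is in.

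This matters for two reasons. First, clues accumulate. An impression formed from one participant's symptoms or comments says something about every other participant with the same code. Second, any disclosure spreads. If one participant's product becomes known for any reason, so does everyone else's.

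The outcomes at stake differ in how exposed they are. Motivation (the MPAM-R questionnaire, the proposed mediator) and symptoms are self-reported. Adverse-event relatedness is a judgement. The primary outcome, median daily steps, is recorded by a device, but it is behaviour: staff give each participant a step goal and stay in contact, so knowledge of the arm could affect it less directly. Inflammatory markers are protected at the assay by Section 4.6.

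**Working it through.** The plan gives no figure on this point, so there is nothing to reproduce. The check is a reading of the text followed by a count.

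**Step 1. What the label scheme is.** Section 3.6 speaks of a letter or number, in the singular, for placebo, different from that of the blueberry powder. Sections 4.6, 5.2, 5.3, 8.2, 8.4 and 8.5 were read for anything that changes this. None describes participant-specific numbers, more than one code per arm, a change of code between waves, a named key holder or a way to unblind one participant alone. One code per arm is therefore an inference, but it is the natural one.

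**Step 2. Effect of one decoded label.** Inputs: 40 randomized, 20 per arm (6.4); waves of 16 and 24 (4.2).

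- Two arm-level codes: decoding one code decodes the other. Assignments made certain = 20 + 20 = 40 of 40.
- Same scheme, decoded after wave 1 has finished: 40 − 16 = 24 participants still have outcomes that can be influenced.
- Participant-specific codes: 1 of 40 certain. If block membership is also known, each of the other 3 in that 2:2 block is in the opposite arm with probability 2/3, and the other 36 stay at 1/2. Expected correct guesses = 1 + 3 × 2/3 + 36 × 1/2 = 21 of 40, against 20 by pure guessing.

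**Step 3. How a shared code lets clues add up.** This is an illustration. Assume that each participant gives staff one independent impression of which code is blueberry, correct with probability q, and that staff follow the majority of k impressions, with ties split evenly:

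P(correct) = Σ over x > k/2 of C(k,x) qˣ(1−q)ᵏ⁻ˣ, plus half the probability of x = k/2.

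| q (assumed) | k = 1 | k = 16 (wave 1) | k = 40 (all) |
|---|---|---|---|
| 0.55 | 0.55 | 0.654 | 0.736 |
| 0.60 | 0.60 | 0.787 | 0.898 |
| 0.70 | 0.70 | 0.950 | 0.996 |

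The documents supply no value of q, and real impressions would not be fully independent. The table shows only the direction: under a shared code weak clues combine, whereas under unique codes each clue bears on its own participant and the k = 1 column applies.

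**Step 4. Size of the labelling task.** 2 packets/day × 7 days × 12 weeks = 168 packets per participant; 168 × 40 = 6,720 packets.

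**The case against.** The best case for the plan has four parts.

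*The text is brief and a manual exists.* Section 3.6 is not a labelling specification. Operational detail is assigned to a manual of procedures that is not among the documents, and it may already provide participant-level codes. That is possible, and if so one sentence in 3.6 settles the point. As written, the protocol says otherwise.

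*The 40 of 40 is a worst case.* It needs a code to be broken early enough to matter, and to become known to people who can influence outcomes. The documents describe no code break: under Section 8.5 a product-related serious adverse event leads to the participant's discontinuation, not to unblinding, and Section 8.4 anticipates no serious events. Section 8.2 also expects little gastrointestinal distress from this amount of fiber if the powder is taken alone, so the clue may be weak. All of this stands, and it is why the figure is given as an upper limit.

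*The outcomes are partly shielded.* Steps come from an accelerometer, the step goal is a fixed 20% increase delivered with scripted wording, and assays are de-identified. Bias in self-reports mainly requires participants, not only staff, to learn their arm. This narrows the route but leaves symptoms, motivation and adverse-event attribution exposed.

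*Two stronger readings do not hold.* A reader might infer that neighbours in shared housing could discover their arms by comparing packets. Two people drawn at random hold different codes with probability 20/39 = 51%, but the comparison shows only same arm or different arm, never which arm is blueberry. Section 4.1 describes a mailing to "seven supportive housing facilities (over 3,000 residents" as one of several recruitment routes; it does not show that neighbours would both be enrolled. A reader might also infer that the fixed blocks weaken the blind further, because "For every block of 4 participants, 2 will be randomized to consume the placebo powder". Under two codes staff already see each participant's code on the packet, so the block adds nothing, and a 2:2 block is symmetric in the two codes and cannot show which is active. Each wave is also recruited before it is randomized, which limits any use of the pattern at enrolment.

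**Conclusion.** The point holds as a weakness in how the blind is built. Taken as written, Section 3.6 gives each arm one code, and the study team that sees those codes also collects symptoms and judges relatedness. One decoded label would expose at most 40 of 40 assignments, with 24 still open to influence if wave 1 is complete, against 1 of 40 under unique codes.

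This rests on two assumptions: that the singular label in 3.6 means one code per arm, and that a decoded label becomes known to people who can affect outcomes. The pooled-clue figures are illustrative and depend on an assumed q. The documents do not show that the blind will be lost, and the plan does not contradict itself here. It is a design choice for which a better and inexpensive alternative exists, and it should be changed because a blind lost through a shared code cannot be restored.

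**What to change.** In Section 3.6, replace the arm-level label with participant-specific codes printed on the individual 24 g packets. A number on the outer kit alone achieves nothing if the packets inside still carry an arm code. State that no code is shared by a whole arm, and that the key is held by someone with no participant contact.

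If that is not practical, the minimum is several codes per arm that change between waves. For example, two codes per arm in each wave would cover 8/2 = 4 participants per code in wave 1 and 12/2 = 6 in wave 2. This is weaker than unique codes: once one of the four codes in a wave is known, two of the remaining three belong to the opposite arm, so those codes are still partly informative.

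The cost is labelling and tracking 168 packets per participant, 6,720 in all, to be arranged before each wave is dispensed. The documents do not say who packages or labels the powder, so the sponsor should confirm who would do this. No visit, procedure, sample size or analysis changes. If the manual of procedures already specifies such codes, the change is one sentence in 3.6.
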